### **2.2 Secondary Outcomes**

1. Compare IIEF outcomes between control and treatment groups at 6 months
2. Compare penile curvature changes in control men at baseline and 12 months (i.e. prior to and following cross-over to CCH)
3. Compare penile length changes in control men at baseline and 12 months (i.e. prior to and following cross-over to CCH)
4. Compare PDQ changes in control men at baseline and 12 months (i.e. prior to and following cross-over to CCH)
5. Compare IIEF changes in control men at baseline and 12 months (i.e. prior to and following cross-over to CCH)
6. Compare penile length changes between control and treatment groups at 6 months
7. Report adverse events at 6 and 12-month time points

8. Report changes in penile curvature between 6 and 12-month assessments for CCH men

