**Study Summary**

Title	Efficacy of a Novel Collagenase Clostridium Histolyticum Protocol for Peyronie's Disease Among Prior Non-responders: A Randomized, Controlled, Single-blinded Study
IRB Protocol Number	20213914
Methodology	Prospective, randomized, controlled, single-blinded
Overall Study Duration	2 years
Subject Participation Duration	1 year
Objectives	Compare key clinical outcomes between controls and men treated with a novel CCH protocol among men previously unresponsive to CCH administration.
Number of Subjects	40
Diagnosis and Main Inclusion Criteria	Men >18 years of age with Peyronie's Disease, current curvature of 30 degrees or more, prior treatment with 6-8 injections of CCH, and prior minimal (<20% and/or <10 degrees) responsiveness to CCH administration.
Randomization	Patients will be randomized 1:3 to control (no treatment) or CCH (up to 8 injections). Patients in the control arm will subsequently be crossed over to CCH treatment after 6 months. Randomization tables will be created and pre-stratified based on baseline penile curvature.
Follow-up Period and Assessments	Men will have objective assessments of curvature and length and standardized and non-standardized questionnaires obtained at various time points (baseline, 6-weeks following completion of CCH, and at the end of the no treatment phase).
Statistical Methodology	Stratification of subjects prior to randomization to assure an equal representation based on baseline penile curvature (30-44, 45-59, 60-74, 75-89, 90 or above). Statistical comparisons between groups and to baseline will be made of responses to subjective questionnaires and objective measures.
Plan for Publication	It is anticipated that the primary study will be published following accumulation of data out to 1 year. Pending novelty of findings, additional studies may also be published if felt to be warranted (subset analyses).

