### 1.2 Investigational Treatments

The current study would randomize men 1:3 into one of two treatment cohorts: 1. Observation followed by CCH or 2. CCH followed by observation. This study design offers the benefits of a randomized,

controlled trial (highest level of evidence), while also providing data for a second set of publications evaluating the cross-over to treatment phase (for controls). RCTs are particularly important in PD, where the disease changes over time in a percentage of men as a function of its natural history. This would also allow blinding of measurements using photographs (single-blinded assessments), which provides further study rigor. See Figure 1 for overall study schema.

1. No treatment (control) followed by CCH. Men in this cohort would undergo baseline assessments followed by no treatment for 6 months and then repeat assessments. Men would then cross-over to CCH treatment and undergo up to 8 injections (or until curvature is <15 degrees). Interval assessments would be performed with the 1st injection of each series, and final assessments would then be performed 6 weeks following the final injection.
2. CCH followed by no treatment. Men in this cohort would undergo baseline assessments followed by up to 8 injections of CCH (or until curvature is <15 degrees). Interval assessments would be performed with the 1st injection of each series and 6 weeks following completion of treatment. Men then would not undergo any additional treatments for 6 months, after which final assessments would then be performed.

During CCH administration, several key differences from the IMPRESS protocols would be performed. Please note that each of these changes have been slowly implemented in the investigators' practice over time to improve overall efficacy of therapy:

	IMPRESS Protocol	Current Study Protocol
Amount administered	0.58 mg	0.9 mg
Suspension volume	0.37 ml	0.7 ml
Method of injection	Into plaque	To point of maximal curvature in the tunica, as determined with an erection at the first injection of each series
Administration schedule	1-3 days apart	1 day apart
Mechanical device traction	None	RestoreX 30-60 min daily until 6 weeks after final injection
Office modeling	Performed 1-3 days after initial injections (defined as "firm")	10-15 lbs of force performed at the time of 2 nd injection

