### 3.5 Study Schema

Patients meeting criteria who have consented will be randomized to either control or CCH x 6 months, followed by a cross-over phase where controls will receive CCH. See Figure 1 for full study schema.

1. Control. Men in this cohort would undergo baseline assessments followed by no treatment for 6 months and then repeat assessments. Men would then cross-over to the CCH treatment phase and undergo up to 8 injections (or until curvature is <15 degrees, whichever comes first). Final assessments would then be performed 6 weeks following the final injection.
2. CCH followed by observation. Men in this cohort would undergo baseline assessments followed by up to 8 injections of CCH (or until curvature is <15 degrees). Assessments would then be performed 6 weeks after completion of treatment. Men then would not undergo any additional treatments for 6 months, after which they would have final assessments performed.

The following table provides an overview of the objective and subjective questionnaire administration:

	Baseline	1 st CCH of each series	6-weeks after CCH completed	End of no treatment phase
Baseline disease specific questionnaire	X			
Baseline subjective questionnaire	X			
IIEF	X	X	X	X
PDQ	X	X	X	X
1 st injection Xiaflex questionnaire		X	X	

Post Xiaflex subjective questionnaire			X	
Post no treatment subjective questionnaire				X
Length measurement	X	X	X	X
Curve measurement	X	X	X	X
Penile ultrasound	X			

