### **5.2 Statistical Analysis**

The current study is considered exploratory in nature. Analyses will be performed using comparisons within and between patient cohorts. All captured data will be utilized as a point of comparison based on accepted standards (e.g. IIEF subdomains, PDQ subdomains, etc.). All data will be analyzed to determine if it is normative / non-normative and will be described and compared appropriately (mean, SD versus median, IQR).

Patients with partial missing data will have all available data included for analysis, with no attempts made to statistically replace missing variables. All data will be analyzed using an intent-to-treat analysis.

Adverse events will be reported as a total as well as compared between cohorts.

A power analysis was performed using historical data from another one of the investigators' RCTs to determine the standard deviation for control men between two sequential assessments. Results of absolute curvature improvements demonstrated a standard deviation of 16 degrees or 27% relative improvement. Using a 0.05 alpha threshold, power of 80%, and expected cohort size of 30 (assuming 30 with 6-month data) this would allow us to distinguish differences over 17 degrees or 29%. Given the investigators' current improvements of 60% with the investigators' preliminary data, we would expect this study to have sufficient power to demonstrate a clinically and statistically significant finding.

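### Secondary outcomes 2 to 5 measure control men from baseline, so the before/after-CCH change includes six untreated months

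*Combined protocol and SAP*

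**What the plan says.** Section 2.2, item 2 is to "Compare penile curvature changes in control men at baseline and 12 months (i.e. prior to and following cross-over to CCH". Items 3, 4 and 5 repeat the time points and the gloss for penile length, PDQ and IIEF.

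The order of events in the control arm is set out elsewhere. The Study Summary says "Patients in the control arm will subsequently be crossed over to CCH treatment after 6 months". Section 1.2 says "Men in this cohort would undergo baseline assessments followed by no treatment for 6 months and then repeat assessments". Section 3.5 continues "Men would then cross-over to the CCH treatment phase and undergo up to 8 injections", and then "Final assessments would then be performed 6 weeks following the final injection". The assessment table in section 3.5 marks curvature, length, PDQ and IIEF at baseline, at the first CCH injection of each series, six weeks after CCH is completed, and at the end of the no-treatment phase.

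On purpose, section 1.2 says the design supplies data for a second set of publications "evaluating the cross-over to treatment phase (for controls". It justifies a randomised trial by describing Peyronie's disease as a condition "where the disease changes over time in a percentage of men as a function of its natural history".

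Section 5.2 calls the study exploratory and states "All captured data will be utilized as a point of comparison based on accepted standards". It does not name a reference visit for items 2 to 5.

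**The concern.** The gloss in items 2 to 5 presents the comparison as before versus after cross-over to CCH. A reader will take the result as the change produced during the CCH phase. The starting point, however, lies six untreated months before that phase, and a later pre-treatment assessment exists. Any change over those months, from natural history or from regression to the mean after selection on curvature, is counted as part of the before/after-CCH result. By the plan's own account the disease changes over time in some men.

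At stake is the figure reported for the cross-over phase in the control men, for which separate publication is foreseen. The six-month between-arm comparisons in section 2.1, and items 1 and 6 of section 2.2, do not depend on this contrast.

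**Working it through.** The plan gives no numerical figure for this contrast, so there is none to reproduce. The check compares the visit schedule with the outcome definitions and then bounds what can be bounded.

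**1. Visits in the control arm (sections 1.2 and 3.5)**

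| Visit | State of the man | Measures |
|---|---|---|
| Baseline | Before the untreated phase | Curvature, length, PDQ, IIEF |
| End of no treatment (6 months) | Before cross-over to CCH | Same four |
| 6 weeks after CCH completed (nominal 12 months) | After CCH | Same four |

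Items 2 to 5 use the first and third rows. The CCH phase lies between the second and third. The only 6-to-12-month contrast in section 2.2 is item 8, which covers CCH-first men and curvature alone.

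**2. Identity**

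Change(0 to final) = change(0 to 6, untreated) + change(6 to final, CCH phase).

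The two contrasts agree on average only if the mean untreated change is zero. As an illustration with assumed values, a true CCH-phase change of −17 degrees would appear as −17 + 5 = −12 with an untreated drift of +5, and as −17 − 5 = −22 with a drift of −5.

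**3. Number of men**

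Allocation is 1:3 (Study Summary). Of 40 enrolled, 40/4 = 10 are controls. Of 30 with outcomes, 30/4 = 7.5, so 7 or 8.

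**4. Regression to the mean from the 30-degree entry criterion**

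All inputs are assumed. Observed curvature is taken as normal and truncated below at 30 degrees, and the baseline reading is taken to be the qualifying one. The underlying mean is solved so that the mean after selection is m. The expected fall on remeasurement is

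(error SD² / observed SD) × φ(z) / (1 − Φ(z)), with z = (30 − underlying mean) / observed SD.

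Example: error SD 8, observed SD 20, m = 50 gives an underlying mean of 39.62, z = −0.481 and a ratio of 0.519. Then (64/20) × 0.519 = 1.66 degrees.

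| Error SD, observed SD | m = 50 | m = 55 | m = 59 | m = 65 |
|---|---|---|---|---|
| 4, 15 | 0.28 | 0.14 | 0.08 | 0.03 |
| 8, 20 | 1.66 | 0.99 | 0.66 | 0.35 |
| 11.3, 25 | 4.06 | 2.65 | 1.91 | 1.17 |

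The value 11.3 is 16/√2. It treats the whole of the 16-degree SD in section 5.2 as visit error and is an upper case. An m of 59 is about what 16 degrees equalling 27% would imply (16/0.27 = 59.3). This component looks like improvement. Natural-history change comes on top of it and is not quantified in the documents.

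**5. Could the trial show that drift is negligible?**

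Apply the section 5.2 SD of 16 degrees between two control assessments. The 95% half-width for the mean untreated change is t × 16/√n:

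- n = 10: 2.262 × 16/√10 = 11.4 degrees
- n = 8: 2.365 × 16/√8 = 13.4 degrees
- n = 7: 2.447 × 16/√7 = 14.8 degrees

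This is sampling uncertainty, not an estimate of bias. It shows that so few men could not establish that drift is small.

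**6. How much drift a six-month reference removes**

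If drift were steady (an assumption) and the final assessment came L months after the six-month visit, the share removed is 6/(6 + L):

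| L (months, assumed) | 4.5 | 6 | 7.5 | 9 |
|---|---|---|---|---|
| Share removed | 57% | 50% | 44% | 40% |

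The rest remains in the CCH-phase change.

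**The case against.** The strongest reply is that nothing here is false. Baseline does precede cross-over, and baseline-to-final change is a valid description of a control man's whole course. Section 1.2 describes what the data can support later; it does not define the quantity for items 2 to 5. The word for changes in those items might mean change before cross-over against change after it, which would use the six-month visit. Section 5.2 promises to use all captured data. No non-zero mean drift is shown in these prior non-responders, the only component that can be bounded is probably small, and the proposed reference removes only part of a steady drift.

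Much of this stands. There is no contradiction in the text, material bias is not demonstrated, and the matter is confined to secondary outcomes in an exploratory study. What does not stand is the suggestion that the plan already covers the point. The items name baseline and 12 months, and those two time points do not define a comparison of untreated with treated change. Section 5.2 permits use of the six-month value without making it the reference, so the choice could be made after the results are seen.

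One further point is fair: the four measures are also scheduled at the first injection of each series, so there may be two pre-CCH readings. The plan has to name one.

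**Conclusion.** The concern holds. As written, items 2 to 5 add the untreated 0-to-6-month change to the CCH-phase change, and no listed outcome gives the six-month-to-final contrast in control men. The bias relative to the CCH-phase change equals the true mean untreated change, whose size and sign the documents do not give. The regression-to-the-mean part is probably small: 0.3 to 1.7 degrees with error SD 8 and observed SD 20, 0.1 to 1.9 degrees across the SD pairs at a mean of 59, and 0.03 to 4.1 degrees over every assumed combination. These figures rest on a normal model and assumed inputs.

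Confidence is high for the reading of the schedule and the identity. It does not extend to any particular size of bias. The change should be made because it is a free improvement; the trial's main comparison is not at risk.

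**What to change.** Reword section 2.2, items 2 to 5, as follows:

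- **Main contrast:** the paired within-man change from the end-of-no-treatment assessment to the assessment six weeks after CCH completion, for curvature, length, PDQ and IIEF. Name the visits by event, since the final visit is tied to the last injection and 12 months is nominal. If the first-injection assessment is a separate visit, say that it is not the reference.
- **Natural history:** report the baseline-to-six-month change in the same men separately.
- **Whole course:** keep the baseline-to-final change as a descriptive summary, labelled as covering both phases.
- **Interpretation:** add one sentence saying that the six-month-to-final contrast is an uncontrolled pre-post change and may carry drift during the CCH phase.

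The cost is the wording of four secondary outcomes and one sentence. All four measures are already scheduled at both visits in section 3.5, so no data, visits or patients are added and the primary comparisons do not change.

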### **3 Study Design**

#### **3.1 Subject Selection**

##### **3.1.1 Inclusion Criteria**

- Men with PD
- >18 years old
- Curvature  $\geq 30$  degrees
- Previously completed 6-8 CCH injections
- Prior minimal (<20% and/or <10 degrees) responsiveness to CCH administration
- Prior CCH injections must have been performed without use of a Restorex traction device and used the IMPRESS protocol
- Ability to achieve an erection satisfactory for intercourse with or without PDE5 inhibitors
- The patient exhibits a palpable plaque consistent with Peyronie's Disease

##### **3.1.2 Exclusion Criteria**

- Prior surgical treatment on the penis (other than circumcision)
- Any contraindications to CCH – as determined by the PI
- Inability to complete 8 additional CCH injections
- Severe plaque calcification (i.e. >1 cm shadowing)

#### **3.2 Setting and Investigator**

The current study will be conducted by CURE PD, a charity established to conduct studies in men with PD. All treatments will be performed at the Male Fertility and Peyronie's Clinic in Orem, UT by [name].

[name] is the former head of male infertility and Andrology at the Mayo Clinic in Rochester, MN, and he has previously completed several investigator-initiated randomized, controlled trials.

#### **3.3 Recruitment**

Men who are seen in the Male Fertility and Peyronie's Clinic for Peyronie's Disease and who have prior histories of CCH administration with minimal / no improvements will be offered entry into the trial at the time of their clinical visit. Additional recruitment will be performed by contacting other PD providers around the country and through advertising in common PD forums.

### 3.4 Consent and Enrollment

Patients attending the Male Fertility and Peyronie’s Clinic or noting interest via email will receive a description of the study. Those interested in participating, will be given the opportunity to meet with the study coordinator to further review study details and formal consent.

Patients that would like additional time to consider their participation will be given another opportunity to meet with the study coordinator at a later time. If the patient expresses interest in participating at any time, a formal consent will be reviewed.

At enrollment, all participants will be assigned a study identifier, with a master list maintained in a password protected database linking the patient to the identifier. A total of up to 40 patients will be enrolled to achieve outcomes of at least 30 men (total study power 40 given that each participant will serve as a control as well as treatment comparator).

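### Section 3.4 credits the trial with an effective size of 40 because every man serves as his own control, but only the 7 to 10 control-arm men are observed untreated before CCH

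*Combined protocol and SAP*

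**What the plan says.** Section 3.4 sets the numbers: "A total of up to 40 patients will be enrolled to achieve outcomes of at least 30 men". A parenthesis then adds "total study power 40 given that each participant will serve as a control as well as treatment comparator".

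The rest of the plan describes the design as follows.

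- **Allocation.** The Study Summary has "Patients will be randomized 1:3 to control (no treatment) or CCH (up to 8 injections", and section 1.2 repeats the 1:3 ratio.
- **Crossover.** Section 3.5 describes the initial 6 months as "followed by a cross-over phase where controls will receive CCH". No crossover is described for men who start on CCH.
- **Control arm.** Section 3.5: "Men in this cohort would undergo baseline assessments followed by no treatment for 6 months and then repeat assessments". CCH comes afterwards.
- **CCH arm.** Sections 1.2 and 3.5 start CCH after the baseline assessments. The 6 months without treatment come once CCH is complete.
- **Endpoints.** The primary endpoints (section 2.1) compare the randomised groups at 6 months. Secondary item 2 is "Compare penile curvature changes in control men at baseline and 12 months", and items 3 to 5 do the same for length, PDQ and IIEF, again in control men. Item 8 reports the change in curvature from 6 to 12 months in CCH men.
- **Power.** Section 5.2 uses an "expected cohort size of 30 (assuming 30 with 6-month data" and an SD of 16 degrees or 27%. It gives a detectable difference of 17 degrees or 29%.

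**The concern.** A man serves as his own control for the effect of CCH when he is observed over an untreated period as well as over a treated one, with the untreated period free of the treatment's effect. Section 3.4 says that this is true of each participant and bases an effective size of 40 on it. Under 1:3 allocation with a one-way crossover, it can be true of only about a quarter of the men.

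At stake is what a reader believes about the size of the evidence. Section 1.2 presents the crossover phase as material for further publications, and those analyses would rest on the control arm alone. A reader could also take the parenthesis to mean that the crossover strengthens the primary comparison, which it cannot do.

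**Working it through.** **1. What lies behind the 40.** The plan gives no calculation for it, so it can only be checked by counting men.

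| Way of counting | Result |
|---|---|
| Each evaluable man twice | 2 × 30 = 60 |
| Each enrolled man twice | 2 × 40 = 80 |
| Evaluable men, with evaluable controls counted again | 30 + 30/4 = 37.5 |
| Evaluable men, plus enrolled controls | 30 + 40/4 = 40 |

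Only the last row reaches 40 by double counting. It mixes evaluable and enrolled men, and it counts only controls twice, which contradicts the reason given. The figure may simply repeat the number enrolled, but then the reason attached to it explains nothing.

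**2. Who has an untreated period before CCH.**

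- Of 40 enrolled: 40 × 1/4 = 10 control, 40 × 3/4 = 30 CCH first.
- Of 30 evaluable: 30 × 1/4 = 7.5 (7 to 8) control, 30 × 3/4 = 22.5 (22 to 23) CCH first.

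The CCH-first men contribute a change from baseline to after treatment and a later change from 6 to 12 months. The first is a treated change. The second follows treatment and describes durability. Neither is an untreated control observation.

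**3. Effect on the primary comparison.** It is made between groups at 6 months, before control men receive CCH. Data collected after crossover come later and add nobody to it.

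**4. The plan's own power figure.** A two-sample t-test, two-sided 0.05, 80% power, with 30 men split 15:15, gives 16.96 degrees and 28.61%. These round to the stated 17 and 29%. A one-sided test with 30 men at 1:3 (7.5:22.5) gives 17.19 degrees and 29.02%, which also fits. A two-sided test with 10:30 gives 16.80 degrees and 28.34%, which rounds to 17 and 28%. The plan does not say which split or sidedness it used, but it does state 30 men.

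**5. What the before/after-crossover comparison can detect.** For a paired t-test, solve for the change δ in

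1 − F(t(0.975, n−1); n−1, δ√n / SD) = 0.80

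where F is the noncentral t distribution function with n−1 degrees of freedom. SD is 16 degrees or 27% (section 5.2), carried over to change after CCH by assumption.

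| Control-arm men | Detectable change |
|---|---|
| 7 | 20.4 degrees / 34% |
| 8 | 18.5 degrees / 31% |
| 10 | 15.9 degrees / 27% |

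**The case against.** The strongest reply has four parts.

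- **The 40 does no work.** Section 5.2 computes with 30, the same 30 that section 3.4 gives as the minimum with outcomes. The parenthesis changes no endpoint, analysis or enrolment target. This stands, and it limits the point to a wrong statement. A reader might infer from the 10:30 result above that the power calculation really used 40. The documents do not support that: they state 30, and the 10:30 figures fit the stated 29% less well than the 15:15 figures do.

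- **Control may be meant loosely.** Every man has a baseline and a no-treatment phase, the Study Summary plans comparisons to baseline, and section 5.2 plans comparisons within cohorts. This stands in part. A reader might infer that all within-man analyses are confined to the control arm. They are not: item 8 of section 2.2 concerns CCH men, and change from baseline is available in both arms. What is confined to control men is the before/after-crossover comparison in items 2 to 5. A change from baseline still has no untreated period to set it against.

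- **The phrase is undefined.** A reader might take it as a claim of a paired test on 40 men and set a much smaller detectable change against the figures above. The documents claim no such test and state no such figure, so that contrast should not be drawn.

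- **The SD is borrowed.** Section 5.2 takes it from control men between two sequential assessments, and response to CCH may vary more or less. If the aim were to compare each man's treated-period change with his untreated-period change, the SD of a difference of two changes would be needed, which the documents do not give. Assuming equal SDs and no correlation, it would be 16√2 = 22.6 degrees, and the detectable changes would be 28.8, 26.2 and 22.5 degrees for 7, 8 and 10 men. The detectable changes are therefore conditional. The counts of men are not affected.

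**Conclusion.** The parenthesis in section 3.4 is wrong as written. Only control-arm men can serve as their own untreated controls: 10 of 40 enrolled, about 7 to 8 of 30 evaluable. The 40 does not follow from the reason given for it, and it is not the 30 used in section 5.2.

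The error is one of description. It does not show that the 17 degrees or 29% was computed from 40 men. Whether that figure suits a 1:3 split is a separate question.

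The counts assume that allocation comes out at exactly 1:3 and that losses fall evenly on the arms. The 30 in section 5.2 refers to men with 6-month data, so further loss during the controls' CCH phase would lower the crossover count. The detectable changes of 20.4, 18.5 and 15.9 degrees also rest on the borrowed SD.

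**What to change.** In section 3.4, delete the parenthesis and state two sizes in its place:

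- the 6-month between-group comparison is sized on about 30 evaluable men, about 7 to 8 control and 22 to 23 CCH;
- the before/after-crossover comparison (section 2.2, items 2 to 5) uses control-arm men only, about 7 to 10.

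A detectable change for the second comparison is optional in a study that calls itself exploratory. If one is given, state the test (paired t, two-sided 0.05, 80% power) and the assumption that the control-men SD of 16 degrees or 27% applies to change after CCH.

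The cost is wording only. No visit, procedure, treatment or enrolment number changes, although the stated size becomes less favourable.
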